### 14.1. DERIVATIONS

Overall percentage of the study intervention compliance will be calculated as follows:

Compliance = number of doses taken/ (number of days on therapy x 2) x 100%

## 15. EFFICACY ENDPOINTS

### 15.1. SECONDARY EFFICACY ENDPOINTS

There are no primary efficacy endpoints defined for this study. The efficacy analysis is defined in terms of secondary and patient diary endpoints.

#### Secondary Endpoints -

- *Early clinical response* at the on-therapy visit (Day 3 to 5), defined in terms of 'success'

Document: \\ieedc-vnasc01\BIOSdata\GSK\BRL25000\PPD  
Author: PPD

\Biostatistics\Documentation\SAP

Version Number: V1.0

Version Date: 18JUL2022

Template No.: CS\_TP\_BS016 Revision 6

Reference: CS\_WI\_BS005

Effective Date: 02Dec2019

or 'failure' to study intervention.

- *Primary clinical response* at the end-of-therapy visit (Day 12 to 14), defined in terms of 'success' or 'failure' to study intervention.
- *Secondary clinical response* at follow-up (Day 22 to 28), defined in terms of 'success' or 'failure' to study intervention.
- Incidence of protocol-defined diarrhea (PDD) in children receiving Augmentin (ES)-600 (AMC/CVA 14:1) at 90/6.4 mg/kg/day in two divided doses administered for 10 days in ARTIs (AOM, ABRS or CABP).

#### Definition of clinical responses

Early or Primary Clinical Response will be defined using following criteria:

Table 3:

Success	Clinical cure	Sufficient resolution or improvement of the signs and symptoms such that no additional antibiotic therapy is indicated.
	Improvement	Improvement in at least 1 presenting sign/symptoms. No additional antibiotic indicated.
Failure	Clinical failure	Non-improvement or deterioration in any sign/symptoms after 2 or more days of therapy. Additional antibiotic therapy is indicated.
	Unable to determine	A valid assessment of clinical outcome could not be made (eg, participant did not attend or consent to clinical examination or lost to follow-up).

The proportion of early and primary response will be calculated as follows-

- Proportion of early response = The number of subject who is categorized as success (clinical cure or improvement) at on therapy (OT) visit / the number of subjects in ITT population
- Proportion of primary response = The number of subject who is categorized as success (clinical cure or improvement) at end of therapy (EOT) visit/ the number of subjects in ITT population

Secondary Clinical response will be described using following criteria:

Table 4:

Document:	\\ieedc-vnasc01\BIOSdata\GSK\BRL25000\PPD	Biostatistics\Documentation\SAP
Author:	PPD	Version Number: V1.0 Version Date: 18JUL2022

Template No.: CS\_TP\_BS016 Revision 6

Reference: CS\_WI\_BS005

Effective Date: 02Dec2019

Success	Persistent clinical cure*	Sufficient resolution of signs/symptoms for those Subjects who were clinically cured or improved at the end of therapy. No additional antibiotic indicated.
Failure	Clinical recurrence	Reappearance of signs/symptoms for those Subjects who were clinically cured or improved at the end of therapy. Additional antibiotic therapy is indicated.
	Unable to determine	A valid assessment of clinical outcome could not be made (eg, participant did not attend end of therapy visit, or extenuating circumstances or lost to follow-up).

\* Subjects who showed 'improvement' at EOT (i.e., clinical 'success') and remained same at FU without requiring additional intervention, will be categorized as 'persistent clinical cure'.

The proportion of secondary response will be calculated as follows-

- Proportion of secondary response = The number of subject who is categorized as success (persistent clinical cure) at follow-up (FU) visit / the number of subjects in ITT population

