^j Local examination refers to ear, nose/paranasal sinus or chest examination depending upon the primary diagnosis ie, AOM, ABRS or CABP

^k Includes assessment of disease at baseline and evaluation of clinical improvement or deterioration at other visits during study, as per Investigator’s discretion.

^l Includes baseline signs and symptoms (other than disease under study).

^m The parent/legal guardian should record the AEs, dosing information, diarrhoea related information in the Dairy Card through the treatment period and until EOT. Patient Diary cards will be appropriately translated for all languages required based on sites participating in the trial.

ⁿ All AEs will be collected from the signing of the ICF until the follow-up visit at the time points specified.

^o The secondary clinical response evaluation will be performed at scheduled FU visit only for participants who were treatment successes at the EOT. This is unlike participants with disease recurrence post EOT, whose secondary clinical response evaluation would have already taken place at interim visit, at the time of recurrence.

^p Incidence of protocol-defined diarrhoea will be assessed (as a secondary endpoint) at EOT (Day 12 to 14), scheduled FU visit (Days 22 to 28) and interim visit, if any.

^q Not required for the participants who were withdrawn from the study intervention due to worsening, or no improvement, or requirement of additional antibiotics during OT visit (Day 3 to 5).

*In case first dose can be given on Day 0 (after laboratory test result availability), the same will be considered as Day 1.

**Rationale for range: Days 3 to 5; 12 to 14; 15 to 21, and 22 to 28: Basis previous GSK studies. Day 15 to 21 is to cover interim period between EOT and FU to factor any disease recurrence. Refer to Section 5.4 for the details of the evaluation to be performed at each visit.

*** Participants with disease recurrence following the EOT visit (Day 12 to 14), but prior to the scheduled FU visit (Day 22 to 28) will be required to visit the study site twice - once during interim visit at time of recurrence (Day 15 to 21) and again at scheduled FU visit (Day 22 to 28). At interim visit all the evaluations which are to be performed at scheduled FU visit, including primary and secondary endpoint assessments will be performed. However, at scheduled FU visit (Day 22 to 28), all evaluations conducted at interim visit will be repeated, except secondary clinical response.

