9.4.3. Secondary Endpoint(s)

Statistical analyses on efficacy endpoints will be conducted using participants from the Intent to treat population. All the displays will be created as overall summaries and as stratified by indication.

Early Clinical Response

The estimand is the proportion of successful clinical responses. The intercurrent events expected for this endpoint are:

- Discontinuation of study treatment due to AE
- Discontinuation of study treatment due to lack of efficacy
- Use of rescue medication
- Discontinuation of study treatment due to any other reason

The estimand strategies for the above intercurrent events are

- A **composite strategy** would be used if intercurrent event '**Discontinuation of study treatment due to AE**' **Discontinuation of study treatment due to lack of efficacy**' and '**Use of rescue medication**' occur. That is, if a subject discontinues the study treatment due to AE or due to lack of efficacy or uses rescue medication, the subject will be imputed as a failure.
- A treatment policy would be used if intercurrent event 'Discontinuation of study treatment due to any other reason' occurs. That is, if a subject discontinues the study treatment due to any other reason (other than AE, lack of efficacy or use of rescue medication), the data for that subject will be analysed as collected

The proportion of clinical response OT (Days 3 to 5) (defined as: A treatment success is defined as either "clinical cure" or "improvement" at end of therapy and treatment failure is defined as a participant whose clinical outcome was "clinical failure" or "unable to determine") with corresponding 95% CI will be calculated. A full description of statistical analysis methods will be mentioned in SAP of study.

Primary Clinical Response

The estimand is the proportion of successful clinical responses. The intercurrent events expected for this endpoint are:

- Lack of compliance (<80%)
- Discontinuation of study treatment due to lack of efficacy
- Discontinuation of study treatment due to AE
- Use of rescue medication
- Discontinuation of study treatment due to any other reason

The estimand strategies for the above intercurrent events are

- A **principal stratum** strategy will be used in case of '**Lack of compliance (<80%)**'. That is, only those subjects who have more than 80% compliance would be considered in the calculation of proportion.

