#### 2. Primary clinical response at end of therapy [EOT (Day 12 to 14)]

- Population:  
Children with acute respiratory tract infections (ARTIs) in India between 6 months to 12 years of either gender.
- Treatment conditions:  
Augmentin (ES)-600 with dose level 90/6.4 mg/kg/day twice daily (12 hourly) for 10 days.
- Variable/Endpoint:  
Proportion of successful primary clinical response at end of therapy (EOT) visit.
- Summary measure:  
Counts and percentages for primary clinical response at end of therapy (EOT) visit with corresponding 95%CI
- Intercurrent events (ICEs):
  - Lack of compliance (<80%) - Principal stratum  
Only those subjects who have at least ( $\geq$ ) 80% compliance would be considered in the calculation for proportion of primary clinical response
    - Discontinuation of study treatment due to AE, discontinuation of study treatment due to lack of efficacy and use of rescue medication - Composite strategy

If subject discontinue due to above mentioned three ICEs, then primary clinical response for that subject will be imputed as a failure.

- Discontinuation of study treatment due to any other reason – Treatment Policy

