#### Rationale for estimand:

Lack of compliance (<80%) will impact on primary clinical response therefore subjects who have at least ( $\geq$ ) 80% would be considered for primary clinical response under principal stratum strategy.

Discontinuation of study treatment due to AE, discontinuation of study treatment due to lack of efficacy and use of rescue medication will affect the primary clinical response thus the primary clinical response will be counted as failure under composite strategy.

The reasoning of treatment policy is to estimate the primary clinical response until subjects are on study will be collected and reported (regardless of the intercurrent event occurring).

No intercurrent event is defined for secondary clinical response endpoint as no events are expected to occur during the follow-up period. The data will be analyzed as collected.

No intercurrent event is defined for Protocol-defined diarrhoea (PDD) endpoint. The data will be analyzed as collected.

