### 3.3. CHANGES TO ANALYSIS FROM PROTOCOL

There is no change in analysis from protocol.

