### 5.2. INTENT TO TREAT POPULATION (ITT)

All Subjects who are enrolled and receive at least 1 administration of the investigational product (Augmentin [ES]-600) will be included in the intent-to treat population. The ITT population will be used for all safety and efficacy analyses.

---

Document:	\\ieedc-vnasc01\BIOSdata\GSK\BRL25000	PPD	Biostatistics\Documentation\SAP
Author:	PPD	Version Number:	V1.0

Template No.: CS\_TP\_BS016 Revision 6      Reference: CS\_WI\_BS005

Effective Date: 02Dec2019

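### Primary clinical response has two conflicting denominators (all ITT, or only children at least 80% compliant), and no rule says which prevails when a composite failure has low or missing compliance

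*SAP*

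**What the plan says.** **All ITT.** SAP 15.1, under the definition of clinical responses, gives the primary response proportion as the number of successes "at end of therapy (EOT) visit/ the number of subjects in ITT population". SAP 5.2 adds: "The ITT population will be used for all safety and efficacy analyses".

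**Compliers only.** SAP 2.2 treats compliance below 80% as an intercurrent event with a principal stratum strategy. Only children with at least "80% compliance would be considered in the calculation for proportion of primary clinical response", and the rationale repeats that those with at least "80% would be considered for primary clinical response under principal stratum strategy". Protocol 9.4.3 has the same restriction: "only those subjects who have more than 80% compliance would be considered in the calculation of proportion". That section also opens by assigning the efficacy analyses to the ITT population.

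**Composite rule.** For discontinuation due to an adverse event or lack of efficacy, or for rescue use, SAP 2.2 says "then primary clinical response for that subject will be imputed as a failure". Protocol 9.4.3 agrees.

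**Compliance.** Protocol 6.4 and SAP 14.1 define it as doses taken divided by twice the days on therapy. SAP 14 tabulates three categories, with none for a missing value. SAP 7.3 imputes no missing data.

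**Declared changes.** SAP 3.3: "There is no change in analysis from protocol".

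**The concern.** A child below 80% compliance with no composite event is in the SAP 15.1 denominator and outside the SAP 2.2 calculation. Two programmers following different sections would report different rates and intervals for the same endpoint, and neither would be breaking the plan. In a single-arm, open-label study this proportion and its interval are themselves the efficacy result, so the denominator should be settled before the data are seen.

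The second gap concerns order. If the compliance filter is applied first, a child who stopped for lack of efficacy and has low or no recorded compliance disappears. If the composite rule is applied first, that child counts as a failure. The plan does not choose. Only failures can be lost this way.

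**Working it through.** **1. The plan's own figure.** There is none for this endpoint. The sample size sections give precision only for the TEAE proportion. N = 310 is from protocol 9.2 and SAP 6.8; every other count in steps 3 to 5 is assumed. Intervals are exact binomial, as in SAP 15.1.1.1. Differences are taken from unrounded rates.

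**2. Who could be a composite failure below the cut?** Compliance = doses taken / (days on therapy × 2).
- Stopped after 2 days, no dose missed: 4/4 = 100%.
- Stopped after 2 days, one dose missed: 3/4 = 75%.
- Stopped after 4 days, two doses missed: 6/8 = 75%.
- Full 10 days, four doses missed: 16/20 = 80%, exactly on the cut.

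Stopping early does not by itself lower compliance. The exposed group is early stoppers who also missed doses. A second possible group is children withdrawn at the on-therapy (OT) visit for efficacy reasons. For the compliance assessment, footnote q to the protocol's Schedule of Activities says "Not required for the participants who were withdrawn from the study intervention due to worsening, or no improvement", or because further antibiotics were needed. It does not cover adverse event or diarrhoea withdrawals.

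**3. Denominator conflict alone, base case.** Assume 20 composite failures at OT, 20 other children below 80% (14 successes) and 270 compliant children (250 successes).
- All ITT: (250 + 14)/310 = 264/310 = 85.2% (80.7 to 88.9).
- Compliers, composite failures kept: 250/(270 + 20) = 250/290 = 86.2% (81.7 to 90.0).
- Difference: +1.0 point.

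**4. Direction.** The ITT rate is a weighted average of the kept rate and the success rate in the other non-compliers. The sign therefore depends on which of those two is larger. In the base case, 19 of 20 non-complier successes instead of 14 gives 269/310 = 86.8%, and the difference becomes -0.6. Now vary other non-compliers from 10 to 40, composite failures from 5 to 30 and non-complier success from 50% to 100%, holding complier success near 250/270 = 92.6%:
- Lowest (40 others, all successes; 30 failures): 222/270 - 262/310 = 82.2% - 84.5% = -2.3 points.
- Highest (40 others, 20 successes; 5 failures): 245/270 - 265/310 = 90.7% - 85.5% = +5.3 points.

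**5. Precedence gap alone.** This is measured against the kept figure of 86.2%, so that step 3 is not counted twice.

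| Composite failures dropped | Rate (95% CI) | Change |
|---|---|---|
| 5 of 20 | 250/285 = 87.7% (83.3 to 91.3) | +1.5 |
| 10 of 20 | 250/280 = 89.3% (85.1 to 92.7) | +3.1 |
| 20 of 20 | 250/270 = 92.6% (88.8 to 95.4) | +6.4 |

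The numerator stays at 250 while the denominator shrinks, so this effect has only one direction.

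**The case against.** The best defence is that ITT is the analysis set and the complier group is a subset drawn from it, with the endpoint-specific estimand in SAP 2.2 governing. This is fair against SAP 5.2: the protocol combines the same two statements, so the SAP inherits the tension. A reader might infer that the SAP silently departed from a clean complier rule in the protocol; protocol 9.4.3's own opening does not support that. The defence fails for SAP 15.1, which prints the denominator. It is the same one used there for early response, which has no compliance event. The SAS code in SAP Appendix 3 shows no compliance filter that would settle the matter.

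On the precedence gap, the instruction to impute a failure most naturally means the child is counted. Footnote q says only that compliance is not required. Protocol 4.1 and 5.4.3.2 and SAP 3.1 list compliance among the OT assessments, the Schedule of Activities has diary review at that visit, and protocol 4.1 turns the visit into EOT with all EOT evaluations for children withdrawn there. A value may well exist. All of this stands and narrows the gap. It does not close it, because a child at 75% is still subject to two unconditional rules.

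**Conclusion.** The contradiction between SAP 15.1 and SAP 2.2 is plain on the page and should be fixed. The missing precedence rule is a real but narrower gap. It affects composite failures who also missed doses and, possibly, OT efficacy withdrawals without a compliance value.

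The true size is unknown because the documents give no response, failure or compliance rates. Under the assumptions shown, the denominator choice moves the rate by about -2.3 to +5.3 points, and dropping composite failures adds up to 6.4 points in the base case.

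Two stronger readings are not supported. One is that the complier denominator necessarily flatters the drug: with composite failures kept, the sign depends on how non-compliers fare, which is not known. The other is that all OT failures will drop out: that needs every one of them to have compliance below 80% or missing, which the documents do not establish.

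The endpoint is secondary and descriptive and protocol 9.1 states no formal hypothesis, so neither error rates nor power is affected.

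**What to change.** Change the SAP only. Make SAP 2.2 and 15.1 state one denominator for primary clinical response, in one of two ways:
- correct the 15.1 formula to the at-least-80% compliance estimand and show the all-ITT proportion as a supplementary table; or
- keep ITT in 15.1, revise 2.2 to match, show the at-least-80% proportion as supplementary, and record the departure from protocol 9.4.3 in SAP 3.3.

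In either case add one sentence: participants with a composite event count as failures and stay in the denominator whatever their compliance value, including when it is missing.

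Two tidying edits can wait for the next protocol amendment, if there is one, since amendments need ethics committee approval. First, protocol 9.4.3 requires compliance above 80%, while its own event definition (below 80%) and the compliance rules elsewhere make 80% inclusive; align it with the inclusive cut. Second, reconcile footnote q with protocol 4.1 and 5.4.3.2 on whether compliance is assessed at OT.

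The cost is a few lines of SAP text and one extra table, with no new data. The reported rate may move slightly in either direction.

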#### Definition of Protocol-defined diarrhoea (PDD)-

The incidence of Protocol-defined diarrhoea (PDD) will be determined based on following rules:

- 3 or more watery stools in one day OR
- 4 or more loose/watery stools in one day OR
- 2 watery stools per day for two consecutive days OR
- 3 loose/watery stools per day for two consecutive days

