Safety profile of AMC/CVA is also well understood. The most frequently reported adverse events are GI disturbances, including diarrhoea, nausea, vomiting and indigestion that can be reduced by taking AMC/CVA with food.[[Stein GE et al, 1984](#)] [[Easton J et al, 2003](#)] High-dose AMC/CVA (90/6.4 mg/kg/day) has shown similar tolerability profile to a conventional twice-daily regimen (45/6.4 mg/kg/day).[[Bottenfield GW et al, 1998](#)] Adverse events (AEs) were reported in a total of 50.2% and 47.3% of patients, with protocol-defined diarrhoea in 11% and 8.8% patients. The most frequently reported adverse events in 521 children treated with the high-dose formulation in another study were diaper rash (4.0%), diarrhoea (3.6%), vomiting (2.3%) and other rash (1.3%). Events probably or possibly related to the medication were documented in 14% of patients.

In summary, Augmentin ES-600 (AMC/CVA 14:1) has been developed based on a combination of PK/PD considerations, in vitro, in vivo animal, and clinical data, and primarily intended to treat ARTIs in cases where PRSP is suspected and beta-lactamase producing organism cannot be ruled out. Its safety profile is well understood and is comparable to conventional Augmentin dosing regimens.

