5.4.5. Post Therapy

5.4.5.1. Interim Visit (Day 15 to 21)

This visit shall occur between the EOT and Follow up Visit (Days 22 to 28) for participants with recurrence of sign/symptoms after EOT visit. Participants will be required to return to the site at the time of recurrence. At post therapy interim visit, the following evaluations will be performed:

- Follow up of ongoing TEAEs (primary endpoint)
- Recording new AEs
- Secondary clinical response (secondary endpoint)
- Incidence of Protocol-defined diarrhea (secondary endpoint)
- Vital signs
- Concomitant medication
- Bowel movements
- Local examination
- Physical examination (assessments of the skin, cardiovascular, respiratory, gastrointestinal, and neurological systems, height and weight)
- Clinical assessment

The participants evaluated at post therapy interim visit, are required to return at scheduled FU visit (Days 22 to 28) for additional safety (not efficacy) assessment.

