8.2. Safety Assessments

Safety is the primary objective of the study.

The primary endpoint of the study is to assess treatment-emergent adverse events (TEAE) in children with AOM receiving Augmentin (ES)-600 at a dose of 90/6.4 mg/kg/day in two divided doses, administered for 10 days.

Incidence of PDD will be evaluated as secondary endpoint, along with efficacy parameters. protocol-defined diarrhea (PDD) is defined as:

- 3 or more watery stools in one day OR
- 4 or more loose/watery stools in one day OR
- 2 watery stools per day for two consecutive days OR
- 3 loose/watery stools per day for two consecutive days.

Participants who withdraw due to diarrhea or has a documented SAE of diarrhea will be considered to have fulfilled the criteria for PDD and will be analyzed as such, even in the absence of Patient Diary card data.

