### **3. STUDY DESIGN**

#### **3.1. GENERAL DESCRIPTION**

This study is an open label, multi-centre, non-comparative study. Subjects will be children aged between 6 months to 12 years, presenting with ARTIs including AOM, ABRS and CABP.

At Preliminary Visit (Day 0) after signing the inform consent form by the parent/guardian and assent form by children between 7 to 12 years of age, a series of screening evaluations will be performed in order to determine whether prospective study participant meets the inclusion criteria. Enrolled and screen passed subjects will receive Augmentin (ES)-600 at 90/6.4 mg/kg/day administered in two divided doses, every 12 hours with food for 10 days.

The incidence of protocol-defined diarrhoea will be determined from information collected from the Patient Diary cards, which will be appropriately translated for all languages required based on sites participating in the trial.

---

Document:	\leedc-vnasc01\BIOSdata\GSK\BRL25000	PPD	Biostatistics\Documentation\SAP
Author:	PPD	Version Number:	V1.0
		Version Date:	18JUL2022
Template No.: CS_TP_BS016 Revision 6		Reference: CS_WI_BS005	

Effective Date: 02Dec2019

After a minimum of two treatment days (four doses) of study intervention has been taken, an 'on-therapy' (OT) visit will be scheduled between Day 3 and 5. During this visit, the investigator/study coordinator shall assess safety (primary endpoint) and 'early clinical response' (secondary endpoint). Safety parameter includes treatment emergent adverse events (TEAEs) for primary study objective. Additionally, clinical status, study intervention compliance, completion of Patient Diary cards, and concomitant medications use will also be assessed. The Investigator will assess safety parameters and clinical status whereas study coordinator will check other parameters with coordinated effort.

Subjects with clinical 'failure' or having PDD or severe AE or SAE at OT visit (Day 3 to 5), will be withdrawn from the study intervention (as per Investigator discretion) and treated appropriately. In such case, the OT visit will be considered as End of Therapy (EOT), and all evaluations that are planned at scheduled EOT (Day 12 to 14) will be completed in this visit. However, these Subjects will return at FU visit (Day 22 to 28) for safety assessment.

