### 15.1.1. ANALYSIS OF SECONDARY ENDPOINT

#### 15.1.1.1. Clinical Response

Frequency and proportion of early, primary, and secondary clinical response will be presented along with 95% CI using exact binomial method

Secondary clinical response statistical analysis will be performed based on as collected data. The following summaries will be generated for early, primary, and secondary clinical response by overall and indication.

- Early clinical response at on-therapy (OT) visit
- Primary clinical response at end of therapy (EOT) visit
- Secondary clinical response at follow-up (FU) visit

Clinical recurrence of disease at follow-up will be summarized with frequency and percentage by overall and indication.

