#### 15.1.1.2. Incidence of protocol- defined diarrhoea (PDD).

No intercurrent event is defined for this endpoint. The data will be analyzed as collected.

Document: \\ieedc-vnasc01\BIOSdata\GSK\BRL25000\PPD Biostatistics\Documentation\SAP  
Author: PPD

Version Number: V1.0  
Version Date: 18JUL2022

Template No.: CS\_TP\_BS016 Revision 6

Reference: CS\_WI\_BS005

Effective Date: 02Dec2019

Frequency and percentage of subjects with incidence of protocol- defined diarrhoea (PDD) will be presented along with 95% CI using exact method (refer SAS code APPENDIX 3)

The following summaries will be generated for incidence of protocol- defined diarrhoea (PDD) by overall and indication.

- Incidence of protocol-defined diarrhoea (PDD)
- Incidence of protocol defined diarrhoea (PDD) over time

Figure for incidence of protocol defined diarrhoea (PDD) over time will also be displayed by overall and indication.

The statistical analysis for incidence of protocol- defined diarrhoea (PDD) will be based on as collected data.

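### The SAP definition of protocol-defined diarrhoea omits the protocol rule that withdrawal for diarrhoea, or an SAE of diarrhoea, counts as a case

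*SAP*

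**What the plan says.** **Protocol.** The four stool-count thresholds for PDD appear in the synopsis and in sections 3, 4.1 and 8.2. Section 8.2 alone adds a further rule: "Participants who withdraw due to diarrhea or has a documented SAE of diarrhea will be considered to have fulfilled the criteria for PDD". The same sentence says these participants are to be analysed accordingly, even where diary card data are absent. Section 9.4.3 plans a count, a percentage and an exact 95% CI for PDD, with the data taken as collected.

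**SAP.** Section 15.1 says "The incidence of Protocol-defined diarrhoea (PDD) will be determined based on following rules" and gives the four thresholds and nothing else. Section 3.1 names the source: "The incidence of protocol-defined diarrhoea will be determined from information collected from the Patient Diary cards". Section 15.1.1.2 adds "No intercurrent event is defined for this endpoint. The data will be analyzed as collected". Section 7.3 says missing data are not imputed. Section 3.3 states "There is no change in analysis from protocol".

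**Timing.** Footnote m to the protocol's Schedule of Activities has the parent or guardian keep the diary through treatment and until the end-of-therapy (EOT) visit. Footnote p has PDD assessed at the EOT visit, the follow-up visit and any interim visit, so assessment continues after the diary has stopped.

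**The concern.** The protocol rule decides who is a case in the analysis, so it belongs in the document from which the PDD table is programmed. An analyst who follows SAP 15.1 would apply the four thresholds to diary records and stop there. A child withdrawn for diarrhoea with a lost or incomplete diary would not be counted. Nor would a child with a diarrhoea SAE after the EOT visit. The protocol counts both.

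The children affected are those whose diarrhoea was serious or ended their participation, which makes them the cases a reader would least expect to be left out of a diarrhoea rate. Because SAP 3.3 reports no departure from the protocol, nothing alerts the reader of the results to the difference.

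**Working it through.** The plan gives no expected rate or precision for PDD, so there is no figure to reproduce. The check is a comparison of the two definitions, followed by the value of one child.

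**Step 1. Direction.** Let S be the children who meet at least one of the four thresholds in the diary data. Let W be those who withdrew due to diarrhoea, and A those with a documented SAE of diarrhoea.

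- SAP PDD = S
- Protocol PDD = S ∪ W ∪ A

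S is contained in S ∪ W ∪ A, so the SAP count cannot exceed the protocol count. With k the number of children in W or A but not in S, the shortfall is k/N.

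**Step 2. Is the extra rule redundant?** It is redundant only if every child in W or A is also in S. The documents do not guarantee that:

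- The diary ends at the EOT visit, while SAEs are collected to follow-up (protocol 8.3.1).
- The protocol wrote the rule expressly for cases without diary data.
- The risk table in protocol 2.3.1 foresees stopping treatment for prolonged or significant diarrhoea without reference to the stool counts.

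**Step 3. Value of one child.** The planned numbers come from protocol 9.2 and SAP 6.8.

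| Group | N | 1/N in percentage points |
|---|---|---|
| Overall | 310 | 0.32 |
| AOM | 136 | 0.74 |
| ABRS | 106 | 0.94 |
| CABP | 68 | 1.47 |

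**Step 4. Illustration.** Protocol 2.2 cites an earlier comparison "with protocol-defined diarrhoea in 11% and 8.8% patients". I read the first figure as the high-dose arm, following the order of the text. The PDD definition used in that study is not shown, so the rate serves only as a scale. 0.11 × 310 = 34.1, so take 34 diary-based cases and add k (assumed). Intervals are exact (Clopper-Pearson), the method the SAP plans.

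| k | Cases/310 | Rate | 95% CI |
|---|---|---|---|
| 0 (SAP count) | 34 | 11.0% | 7.7 to 15.0 |
| 1 | 35 | 11.3% | 8.0 to 15.4 |
| 3 | 37 | 11.9% | 8.5 to 16.1 |
| 5 | 39 | 12.6% | 9.1 to 16.8 |
| 10 | 44 | 14.2% | 10.5 to 18.6 |

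In CABP, 0.11 × 68 = 7.5. Taking 7 cases gives 7/68 = 10.3% (4.2 to 20.1). One more gives 8/68 = 11.8% (5.2 to 21.9), and three more give 10/68 = 14.7% (7.3 to 25.4).

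Overall, even k = 10 moves the estimate by 3.2 points, within the original interval. In CABP three children move it by 4.4 points, also within a wide interval.

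**The case against.** **The gap is close to editorial.** The SAP's four thresholds match the protocol's own definition wherever it is stated, and the as-collected wording follows protocol 9.4.3. The extra rule appears once, in protocol 8.2. PDD is assessed at the on-therapy, pre-EOT interim and EOT visits (protocol 5.4.3.2, 5.4.3.3 and 5.4.4), and PDD is itself a trigger for considering withdrawal. Most children withdrawn for diarrhoea should therefore already meet a threshold. All of this stands, and it is why the shortfall may be zero. It does not remove the mismatch, because protocol 8.2 states how these children are to be analysed and SAP 15.1 states a different, closed list. A general statement of no change does not put a missing rule into the program.

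**The events would still be visible.** Diarrhoea leading to discontinuation and diarrhoea SAEs would appear in the tables of SAP 16.1.2 and 16.1.3. That is correct, and it limits the harm, but those tables do not repair the PDD rate or its interval.

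**Stronger readings that the documents do not support.** A reader might infer that the trial's tolerability result is compromised. No document gives PDD that standing. It is one of several secondary endpoints beside a primary endpoint based on all treatment-emergent adverse events.

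A reader might also extend the point to SAP 15.1.1.1, where "Clinical recurrence of disease at follow-up will be summarized with frequency and percentage by overall and indication", and infer that recurrences rated at the Day 15 to 21 visit are dropped because SAP 6.6 gives that visit its own window. Protocol 8.1 treats the post-therapy interim rating as the secondary clinical response. SAP Table 4 makes recurrence a category of that response, SAP 15.1 defines recurrence without a visit limit, and SAP 3.1 calls these children failures at follow-up. An analyst would sensibly include them, and the table templates mentioned in SAP section 8 are not in the available text. That is at most a wording query.

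**Conclusion.** The SAP's PDD definition is wrong as written, because it leaves out a case rule that the protocol requires and SAP 3.3 reports no departure. The error has one direction: the SAP rate equals or understates the protocol rate.

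The size is k/310 overall and k/68 in CABP. The documents do not give k, and it may be zero. The 11% rate and the values of k from 1 to 10 are illustrative assumptions; the direction and the per-child values do not depend on them. The per-child values assume that enrolment meets the planned numbers.

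The severity is minor. One descriptive secondary endpoint is affected. The primary endpoint and the clinical response proportions are not.

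**What to change.** Add one sentence to the PDD definition in SAP 15.1: a participant who withdraws due to diarrhoea, or has a documented SAE of diarrhoea, counts as PDD regardless of diary data, as protocol 8.2 requires. Apply it in the overall and by-indication tables and the figure of SAP 15.1.1.2. Amend SAP 3.1 so that the diary is not presented as the only source.

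The protocol does not say on which day such a case falls, so the sponsor will need to choose a date convention for the over-time table and figure.

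The cost is a sentence or two of SAP text and a small change to one derivation. Reasons for discontinuation and SAE records are already collected and tabulated under SAP 9.1, 16.1.2 and 16.1.3. The PDD result changes only if at least one child qualifies solely through the added rule.
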